4.1. Overall Design

Consented patients will undergo a screening visit within 28 days of the planned baseline visit. (For women of childbearing potential, a negative serum pregnancy test will be required within 1 day prior to receiving the first dose of study drug). Only those patients who complete screening and meet study eligibility criteria at baseline will be randomized 6:2 to receive phenserine or donepezil in an open-label manner. The first dose of study medication will be taken in the clinic, and the participant will be instructed on how to continue dosing at home until their next visit.

Participants will visit the clinic for safety and other planned study assessments at 2-week intervals through the 8-week treatment period, as detailed in the Schedule of Activities ([Table 1](#)).

Patients who withdraw or discontinue from the study before Week 8 will have an early termination visit within one week of discontinuation that includes safety follow-up. For participants who complete the study, a final follow-up safety assessment will be conducted within one week after completion of dosing.

4.2. Scientific Rationale for Study Design

The randomized, controlled design is required to fully understand the safety and efficacy of phenserine in this cohort. Eligibility requires MCI or mild dementia due to AD based on biomarker confirmation. To ensure safety, the design implements drug titration at different time-points after a detailed unblinded safety-review by the DSMB. The DSMB's role will focus on overall participant safety. Individual dose titration decisions will be made by the site study clinician and Principal Investigator (PI), based on pre-defined criteria. The outcomes include exosome biomarkers, detailed cognitive testing, as well as ADL and fluid biomarker changes.

4.2.1. Patient Input into Design

This project has been presented to the WiseAge reference panel which reviews every study conducted at SESAM, SUS. The feedback has been positive, the panel agrees that there is an unmet need to find new disease-modifying treatments for AD. The panel also underlined the need for safety assessments given the longer duration of treatment compared to previous studies with phenserine and recommended that lumbar puncture and CSF analysis be optional if that is possible. See Appendix 6. for description regarding user involvement.

4.3. Justification for Dose

In the only published phase 2 RCT of phenserine, improvement in cognition was observed in people with AD who received phenserine 15 mg bid for 12 weeks of treatment. In addition, phenserine was generally safe and well tolerated. The proportion of participants who withdrew from the study due to adverse events was just 6% in the placebo arm and the highest dose groups indicating that adequate cholinesterase inhibition in the active arms was likely not achieved. Other methodological issues were identified with the study, prompting the authors to conclude that the full potential of phenserine for AD had not yet been fully evaluated (20)

The most common side-effects observed in prior studies of phenserine were like those associated with other cholinesterase inhibitors and included nausea, vomiting and diarrhoea. The intended maximum dose in this study is similar to the previous clinical studies, and as outlined in the Risk assessment (section 3.2.1) and the study procedures, the distribution in three daily doses, the frequent clinical follow-up assessments, the gradual titration requiring acceptable tolerability, ensures that the safety of the participants is acceptable.

4.4. Study treatment administration

At each visit, participants will receive a clear explanation of the study intervention, including dosing instructions, to ensure accurate understanding and adherence. They will also be provided with a subject diary (see section 11.7 – Appendix 7) to track dosing times assess compliance with the regime and any side effects or adverse events experienced. In addition, participants will be instructed to return all medication bottles at each visit, including any unused medication. The returned medication will be counted and documented by the study staff to cross-verify compliance with diary entries.

A compliance rate between 80% and 120% is considered as acceptable for drug adherence.

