6.3.1. Allocation- procedure to randomize a participant

Both the subjects and the site staff will know which treatment they are assigned. Participants and site staff, will be blinded to the results of the exosomal and blood/CSF biomarker evaluations until the study is completed.

Participants will be identified by a unique study ID. Personal identifiable data (such as name, address, and other contact details) will be collected, but will be stored separately from the research data and will be destroyed as per applicable regulations when the project is concluded. Data will be managed by the University Hospital Stavanger clinical trials unit, following all relevant data protection guidelines and all relevant Clinical Trial Regulations. Data will be collected and stored electronically in accordance with the Data Protection Act 2018 and ICH GCP E6 R2. Data will be cleaned and validated appropriately, with a full Data Protection Impact Assessment (DPIA) undertaken along with development of a comprehensive Data management Plan (DMP) before the first participant is recruited.

[figure not shown]
The computer-generated randomized allocation sequence will be produced by an independent, unblinded statistician and imported into the Viedoc Electronic Data Management System (EDCS). The unblinded statistician will generate randomisation lists using using R v4.2 as implemented in <https://icostatistics.shinyapps.io/randlist/> Participants will be screened for eligibility and first included by study physicians after informed consent. After study inclusion the participant will be randomized via Viedoc. The participant will be allocated treatment arm via Viedoc and receive the assigned IMP treatment at the first baseline visit by a study nurse. The study nurse will record the date of IMP distribution and the time and date of the first dose administered in Viedoc.

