6.5. Study Intervention Compliance

When participants are dosed at the site, they will receive study intervention directly from the investigator or designee, under medical supervision. The date and time of each dose administered in the clinic will be recorded in the source documents. The dose of study intervention and study participant identification will be confirmed at the time of dosing by a member of the study site staff other than the person administering the study intervention.

When participants self-administer study intervention at home, compliance with study intervention will be assessed at each visit, and a subject diary will be completed. Compliance will be assessed by returned capsules/tablets, the subject diary, and during the site visits and documented in the source documents and relevant form. Deviation(s) from the prescribed dosage

regimen should be recorded. Compliance is deemed acceptable if within 80-120% of the scheduled dosing. A record of the quantity of dispensed study intervention to and administered by each participant must be maintained and reconciled with study intervention and compliance records. Intervention start and stop dates, including dates for intervention delays and/or dose reductions will also be recorded.

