9.18. Pharmacokinetics

- Plasma PK samples will be collected at W 2, 4, 6, and 8 visits for all IMP participants. Samples will be analyzed for phenserine to determine C_{max} and t_{1/2}. Available data will be analyzed by the DSMB to assess the safety of ongoing patients. PK samples will also be collected at the Week 8 visit, at peak dose, from all other patients (and at the final maintenance dose level for those who down-titrate due to tolerability) prior to taking the

morning dose, to establish steady-state concentration and stored for later analyses aimed at exploring the relationship between exposure and tolerability/efficacy outcomes.

- Instructions for the collection and handling of biological samples will be provided by the sponsor. The actual date and time (24-hour clock time) of each sample will be recorded. Samples will be used to evaluate the pharmacokinetics (PK) of phenserine. Each sample will be divided into aliquots as described in the SOP. These samples may also be used to evaluate safety or efficacy aspects related to concerns arising during or after the study.

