11.7. Appendix 7: Subject diary

Sample of the subject diary for participants allocated to treatment with phenserine

Deltaker-ID: _____
Studiemedisin: fenserin

Navn på studielege: _____
Sykehus: _____
Telefon: _____

PATH-1 Studien
Behandlingsstudie for tidlig Alzheimer's sykdom
Behandling med fenserin

MEDISINDAGBOK

Deltaker-ID: _____

Formålet med denne medisindagboken er å hjelpe deg med daglig loggføring og oversikt over ditt inntak av studiemedisinen fenserin, som er en medisin under utprøving.

I tillegg kan du legge inn eventuelle bivirkninger eller andre hendelser som oppstår i løpet av behandlingsperioden. Vi vil også gjerne at du oppgir eventuelle endringer i den faste medisineringsplanen din hvis du tar andre medisiner i tillegg til fenserin.

Du vil få en instruksjon på hvordan du fører medisindagbok av studiepersonell på sykehuset.

I tillegg anbefaler vi deg følgende hjelpemidler:

- Dosett/pilleeske
- Sett inn en påminnelse på mobiltelefonen din
- Be din nærmeste pårørende om å minne deg på å ta medisinen din

I tekstboksen på neste side finner du doseringsplanen for behandling med fenserin, samt forholdsregler i tilfelle du glemmer en dose eller du tar for mye.

Deltaker-ID: _____
Studiemedisin: fenserin

Navn på studielege: _____
Sykehus: _____
Telefon: _____

Inntak av fenserin:

Kapselen skal svelges med et glass vann og bør tas sammen med mat. Kapselen skal ikke tygges eller knuses.

Doseopptreppingsplan for fenserin

1. Startdose
2 kapsler 5 mg daglig (1 kapsel morgen og kveld) i 2 uker
2. Dosering fra uke 3:
2 kapsler 10 mg daglig (1 kapsel morgen og kveld) i 2 uker
3. Dosering fra uke 5:
3 kapsler 10 mg daglig (1 kapsel morgen, ettermiddag og kveld) i 4 uker

Eller behandling etter avtale med din studielege

Dersom du har glemt å ta en kapsel

- Dersom du har glemt en dose og det er mindre enn 2 timer siden den skulle ha blitt tatt, kan du ta den glemte dosen.
- Hvis det har gått mer enn 2 timer siden den planlagte dosen, skal du vente til neste dose. Husk å kryss av for glemt dose i dagboken.

Tidsrom mellom dosene:

- 2 kapsler daglig: Ta dosene med et tidsrom på omtrent 12 timer (2 timer tidligere eller senere er akseptabelt).
- 3 kapsler daglig: Ta dosene med et tidsrom på omtrent 8 timer (2 timer tidligere eller senere er akseptabelt).

Dersom du tar for mye av fenserin

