Ved overdosering eller symptomer på overdosering (f. eks. alvorlig kvalme, oppkast, svetting, blodtrykksfall, pustesvikt, kollaps og/ eller krampeanfoll) må du kontakte din studielege (telefonnr.: _____) eller sykehus (telefonnr.: _____) øyeblikkelig.

This is just a sample of the first 4 pages of the diary. The diary will cover the entire treatment period.

Deftaker-ID: _____

Navn på studiefølge: _____

Studiemedisin: faseris

Sykehus: _____

Telefon: _____

Dag dato	Dose	Kryss av for antall kapsler du har tatt	Kryss av for glemt dose	Bivirkninger, symptomer	Endring i fast medisinplan
DAG 0:	 5 mg  10 mg	 1 kapsel morgen  1 kapsel kveld	 1 kapsel morgen  1 kapsel kveld		
DAG 1:	 5 mg  10 mg	 1 kapsel morgen  1 kapsel kveld	 1 kapsel morgen  1 kapsel kveld		
DAG 2:	 5 mg  10 mg	 1 kapsel morgen  1 kapsel kveld	 1 kapsel morgen  1 kapsel kveld		
DAG 3:	 5 mg  10 mg	 1 kapsel morgen  1 kapsel kveld	 1 kapsel morgen  1 kapsel kveld		
DAG 4:	 5 mg  10 mg	 1 kapsel morgen  1 kapsel kveld	 1 kapsel morgen  1 kapsel kveld		
DAG 5:	 5 mg  10 mg	 1 kapsel morgen  1 kapsel kveld	 1 kapsel morgen  1 kapsel kveld		
DAG 6:	 5 mg  10 mg	 1 kapsel morgen  1 kapsel kveld	 1 kapsel morgen  1 kapsel kveld		
DAG 7:	 5 mg  10 mg	 1 kapsel morgen  1 kapsel kveld	 1 kapsel morgen  1 kapsel kveld		

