 **HELSE STAVANGER**
Stavanger University Hospital

SESAM
Regulert kompetensområde for informasjon og utveksling

Delaker-ID: _____ Navn på studielege: _____

Studiemedisin: doseprofil Sykehus: _____
Telefon: _____

Dag dato	Dose	Kryss av her om du har tatt din daglige dose	Kryss av her for glemt dose	Bivirkninger, symptomer	Endring i fast medisinplan
DAG 0: _____	 5 mg  10 mg	 1 tablett	 1 tablett		
DAG 1: _____	 5 mg  10 mg	 1 tablett	 1 tablett		
DAG 2: _____	 5 mg  10 mg	 1 tablett	 1 tablett		
DAG 3: _____	 5 mg  10 mg	 1 tablett	 1 tablett		
DAG 4: _____	 5 mg  10 mg	 1 tablett	 1 tablett		
DAG 5: _____	 5 mg  10 mg	 1 tablett	 1 tablett		
DAG 6: _____	 5 mg  10 mg	 1 tablett	 1 tablett		
DAG 7: _____	 5 mg  10 mg	 1 tablett	 1 tablett		
DAG 8: _____	 5 mg  10 mg	 1 tablett	 1 tablett		
DAG 9: _____	 5 mg  10 mg	 1 tablett	 1 tablett		
DAG 10: _____	 5 mg  10 mg	 1 tablett	 1 tablett		

Próbitt i studie
EU/CT: 2023-010283-00-00 side 2/8 v 1.1, 06.12.2024

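### The protocol relies on the subject diary for dosing times, but the diary has no clock-time field, and no document supplied says where the last home dose before a PK or AChE sample is timed

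*Protocol*

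**What the plan says.** Protocol 4.4 provides the diary "to track dosing times assess compliance with the regime and any side effects or adverse events experienced". Appendix 7 shows sample pages of both diaries:

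- **Phenserine.** Each day has a date, a strength tick, an intake column headed "Kryss av for antall kapsler du har tatt" with morning, evening and later afternoon boxes, missed-dose ticks, and free text for symptoms and medication changes.
- **Donepezil.** The intake column is headed "Kryss av her om du har tatt din daglige dose" and has one box per day. The instructions place intake just before bedtime.

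Neither page has a clock-time field. The times recorded elsewhere are these:

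- Protocol 6.5: "The date and time of each dose administered in the clinic will be recorded in the source documents".
- Protocol 6.3.1: "the time and date of the first dose administered in Viedoc".
- Protocol 9.18, for PK samples: "The actual date and time (24-hour clock time) of each sample will be recorded".

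Protocol 9.18 places PK samples at Weeks 2, 4, 6 and 8. Only the Week 8 sample is tied to a dose, being drawn before the morning dose. Table 1 puts AChE samples at baseline and the same four visits, with no time relative to dose.

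SAP 8.2 plans Cmax, Tmax and AUC if derivable, and plots of exposure against AChE inhibition and exosome markers. SAP 8.3 plans the proportion at or above 45% inhibition, the time to reach it and the duration above it. Neither section mentions time since dose.

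**The concern.** A concentration or percent inhibition can be interpreted only if the time since the last dose is known. The plan records when the PK sample was drawn, but the instrument named for the other half of that interval cannot record it. Before most visits the last dose will have been taken at home.

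The study is meant to inform the Phase 2 dose range. If timing is not recorded, a low value drawn late in the interval cannot be told apart from low exposure, and a participant can fall on either side of the 45% line according to the hour of the blood draw. Times that were not written down cannot be reliably rebuilt later. The 2-hour late-dose rule and the minimum intervals in 4.4.1 also cannot be checked from ticks.

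**Working it through.** The plan states no figure on this point, so there is nothing to reproduce. The steps are a count of samples and a sizing from the protocol's own kinetics.

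**Inputs.** Arms of 12 and 4 (SAP 3). Elimination half-life 6.53 h and Tmax 1.25–1.54 h, taken as 1.5 h; Tmax 2.7 h with food (Protocol 2.3.1, which also says doses are taken with food). Half-life of AChE inhibition 8.25 h (Protocol 4.5, citing a preclinical paper). Dosing bd in Weeks 1–4 and tds in Weeks 5–8 (Table 3).

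**1. Samples.**
- Phenserine PK: 12 × 4 = 48. The Week 8 pre-dose rule covers 12 (reading that sentence of 9.18 as applying to this arm). The other 36 (75%) have no stated time since dose.
- On-treatment AChE: 16 × 4 = 64, of which 48 are phenserine. None has a stated time since dose.
- The Week 8 PK sample still follows an evening home dose whose time is not recorded.

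**2. Fold change in concentration from timing alone.** Fold = 2^(Δt / 6.53).

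| Comparison | Peak at 1.5 h | Peak at 2.7 h (fed) |
|---|---|---|
| Peak versus 8 h | 2^(6.5/6.53) = 1.99 | 2^(5.3/6.53) = 1.76 |
| Peak versus 12 h | 2^(10.5/6.53) = 3.05 | 2^(9.3/6.53) = 2.68 |

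For tds dosing the phenserine diary says "Ta dosene med et tidsrom på omtrent 8 timer (2 timer tidligere eller senere er akseptabelt". A pre-dose sample 6 to 10 h after the last dose therefore varies 2^(4/6.53) = 1.53-fold. For comparison, the single-dose step from 5 to 10 mg is 2-fold.

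**3. Inhibition near the threshold.** A value of 46%, chosen as just above 45%, would read 46 × 2^(−4/8.25) = 33% four hours later. This is illustrative, because the half-life is preclinical. Whether participants reach 46% is a separate question.

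**4. Effect on an exposure-response slope.** Assume sampling time is uniform within each nominal interval: peak to 12 h at Weeks 2 and 4, peak to 8 h at Week 6, and 6–10 h at Week 8. The timing variance of log concentration at each visit is (ln 2 / 6.53)² × width² / 12.
- Peak at 1.5 h: (0.1035 + 0.1035 + 0.0397 + 0.0150) / 4 = 0.065.
- Peak at 2.7 h: (0.0812 + 0.0812 + 0.0264 + 0.0150) / 4 = 0.051.
- Variance from the dose steps, with one visit in four at a 5 mg single dose and three at 10 mg: (ln 2)² × 0.25 × 0.75 = 0.090.
- Between-person variance at an assumed CV of 30%: ln(1 + 0.3²) = 0.086.
- Slope factor: (0.090 + 0.086) / (0.090 + 0.086 + 0.065) = 0.73, and with 0.051 in place of 0.065, 0.78.
- At a CV of 20% the factors are 0.66 and 0.72; at 50% they are 0.83 and 0.86.

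This counts spread within a visit only. Differences between visits in mean sampling time are left out and would lower the factor somewhat.

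**The case against.** The strongest reply is that the documents supplied are not the whole set. Protocol 9.18 says the sponsor will provide collection instructions, several sections refer to SOPs, no eCRF is shown, and the diary pages are marked as a sample. A question about the last dose may already be asked at venepuncture. That stands: a reader might infer that the time is never captured, but the documents support only that nothing in them captures it. The mismatch between 4.4 and Appendix 7 remains either way.

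Three further inferences go too far.

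- **That timing is lost whatever the sampling scheme.** If the visit-day dose is given on site and the sample follows it, 6.5 makes the interval known. Part of the gap is that 9.18 sets no post-dose time for Weeks 2, 4 and 6.
- **That timing adds more variance than the planned dose steps.** Spreading every sample over 1.5–12 h gives 0.104 against 0.090, and a slope factor of 0.63. But dosing is every 8 h in Weeks 5–8 and the Week 8 PK sample is pre-dose. Nominal intervals give 0.051–0.065, below the dose-step variance. Similarly, contrasting 8 h with 15 h before the Week 8 sample exceeds the diary's tds tolerance.
- **That every planned plot is blurred.** PK and AChE share visits, and Protocol 2.3.1 reports a linear relation between concentration and inhibition. If both are drawn together they fall together, and that plot is little affected.

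It is also true that the SAP outputs here are descriptive, so no planned slope estimate is biased. The ticked slot and the diary's tolerance also bound the home dose time roughly.

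**Conclusion.** The point holds in a limited form. The diary shown cannot do what 4.4 assigns to it, and no other instrument in the documents times the last home dose before a sample. With the stated half-life, timing alone can move a concentration about 1.8- to 2.0-fold by 8 h and 2.7- to 3.0-fold by 12 h after intake, and about 1.5-fold for a pre-dose sample within the tds tolerance. The slope factor of 0.73–0.78 rests on nominal intervals, uniform sampling times and a CV of 30%. It shows scale and is not a bias in a planned estimate.

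The consequence falls mainly on the 45% classification with its time-to-target and duration measures, on exposure against exosome markers, and on Cmax, Tmax and AUC. The mismatch between 4.4 and Appendix 7 is certain. Whether the time is really lost depends on SOPs and eCRFs not supplied. The change should be made because it is cheap and missing times cannot be recovered.

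**What to change.** - Add an eCRF field at each PK/AChE visit for the date and time of the last dose before the sample, and whether it was taken with food. Alternatively, add a clock-time entry to the phenserine diary for the doses before each visit. If an SOP already asks for this, cite it in 9.18.
- In SAP 8.2 and 8.3, show concentration and percent inhibition against time since last dose, and label the exposure-response plots by it.
- Reconcile 4.4 with Appendix 7 on what the diary records.
- Reconcile 4.4.1 with the diary. The protocol treats 8 h and 12 h as minimum intervals, while the diary accepts doses 2 h earlier: "Ta dosene med et tidsrom på omtrent 8 timer (2 timer tidligere eller senere er akseptabelt" for three capsules a day and "Ta dosene med et tidsrom på omtrent 12 timer (2 timer tidligere eller senere er akseptabelt" for two.

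The cost is one or two eCRF fields, a line in the SAP, text corrections, and a small recording burden for participants, study partners or the nurse. No dose, visit or sample changes. Redesigning every donepezil intake box is not needed: Protocol 10.3 limits PK analysis to phenserine, and the donepezil diary already places intake at bedtime. Table 2 also names donepezil for PK; if that arm were analysed, the eCRF field would cover it.

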4.4.1. Missed Dose Instructions for phenserine

- If a dose is missed: Participants are instructed to take the dose if it is within 2 hours since the scheduled time. If more than 2 hours have passed since the scheduled dosing time, the participant is instructed to omit the missed dose and continue with the next scheduled dose.. The participant is encouraged to mark the missed dose in the diary.
- Maintaining Safe Dosing Intervals: To prevent excessive dosing, participants should always ensure that a minimum interval is maintained between doses. This interval is 8 hours for three-times-daily dosing, 12 hours for two-times-daily dosing, and 24 hours for once-daily dosing

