Several steps have been taken to ensure safety and tolerability, including a) slow stepwise titration, b) divide the daily dose into three doses eg highest single dose is still 10mg, which reduces Cmax which is the main driver of side-effects, c) ensure IMP is taken with food, and d) frequent in-clinic visit with physical examination and safety laboratory measurements. Any participant who escalates to the highest allowed dose and subsequently experiences intolerable adverse effects will be down titrated to their prior dose level. If more than 2 participants experience dose-limiting side effects at the 10 mg tds dose level, no additional participants will be allowed to dose escalate to that level, and the highest dose that all subsequent participants will be allowed to reach is 10 mg bd.

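### The participant diary permits phenserine doses 6 h (three times daily) or 10 h (twice daily) apart, below the 8 h and 12 h minimum intervals in protocol Section 4.4.1

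*Protocol*

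**What the plan says.** Protocol Section 4.4.1 gives two instructions for phenserine.

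- **Late or missed dose.** "Participants are instructed to take the dose if it is within 2 hours since the scheduled time". Beyond 2 hours, "the participant is instructed to omit the missed dose and continue with the next scheduled dose". That second clause covers the omitted dose only. After a dose taken late, the section does not say whether the next one keeps its original time.
- **Minimum interval.** To guard against overdosing, "participants should always ensure that a minimum interval is maintained between doses". The figures are: "This interval is 8 hours for three-times-daily dosing, 12 hours for two-times-daily dosing, and 24 hours for once-daily dosing".

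The phenserine diary in Appendix 7 (Section 11.7), which is in Norwegian, repeats the late-dose window (less than 2 hours) but gives no minimum interval. For three capsules a day it says "3 kapsler daglig: Ta dosene med et tidsrom på omtrent 8 timer (2 timer tidligere eller senere er akseptabelt"; for two capsules a day, "2 kapsler daglig: Ta dosene med et tidsrom på omtrent 12 timer (2 timer tidligere eller senere er akseptabelt". In English: space the doses by about 8 h or about 12 h, with 2 h earlier or later acceptable.

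Section 6.1 and its Tables 3 and 4 give three phenserine regimens: 5 mg twice daily, 10 mg twice daily and 10 mg three times daily.

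**The concern.** The protocol calls 8 h and 12 h a floor to be kept at all times. The diary calls the same figures a target that may be undershot by 2 h. Participants dose at home from the diary, so those who follow it exactly can depart from the protocol without knowing it.

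Three things make the conflict matter in this trial.

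- Section 2.3.1 supports the tolerability of the highest daily dose partly by its division into three, "which reduces Cmax which is the main driver of side-effects". The spacing of doses is part of that argument.
- Tolerability decides escalation at Weeks 2 and 4 (Sections 6.3 and 6.6). Under Section 2.3.1, more than 2 participants with dose-limiting effects at 10 mg three times daily closes that level to later participants. With 12 participants on phenserine, a few events carry weight.
- SAP Section 3.4.2 counts any departure in study treatment administration as a protocol deviation. Whether a 6 h gap is a deviation depends on which text is applied.

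Short gaps may also go unrecorded. Section 4.4 says the diary tracks dosing times, but the sample pages have tick boxes for morning, afternoon and evening and no field for clock time.

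**Working it through.** This is clock arithmetic; no sample size, power or significance level is involved.

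**Inputs.** Minimum interval m: 8, 12 and 24 h for k = 3, 2 and 1 doses a day (Section 4.4.1). Late-dose window: 2 h (Section 4.4.1). Diary tolerance: 2 h either side of about 8 h or 12 h (Appendix 7). Regimens: k = 2 or 3 (Section 6.1).

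**Step 1: the protocol's own figure.** Even spacing is 24/k: 24/3 = 8 h, 24/2 = 12 h, 24/1 = 24 h. These equal the stated minima. Slack over a day is 24 − k × m: 24 − 3 × 8 = 0 and 24 − 2 × 12 = 0.

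**Step 2: what the diary permits.** Its sentence attaches the 2 h to the interval, so the range is m ± 2.

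**Step 3: late dose with the next dose on its original time.** The gap is m − 2.

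| | Three times daily | Twice daily |
|---|---|---|
| Protocol minimum | 8 h | 12 h |
| Diary range | 8 − 2 = 6 h to 8 + 2 = 10 h | 12 − 2 = 10 h to 12 + 2 = 14 h |
| Dose 2 h late, next dose not moved | 8 − 2 = 6 h | 12 − 2 = 10 h |
| Largest shortfall against the minimum | 8 − 6 = 2 h | 12 − 10 = 2 h |

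**Step 4: late dose with the minimum enforced.** On three doses a day, scheduled times are 0, 8, 16 and 24 h. If the first is taken at 2 h and each later dose waits 8 h, the times are 2, 10, 18 and 26 h. Every dose is 2 h behind schedule, because zero slack gives no way to catch up. If lateness is still judged against the original schedule, any further slip passes the 2 h limit and the dose is omitted. Section 4.4.1 does not say whether the schedule itself moves.

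**Step 5: the once-daily line.** Section 4.4.1 covers phenserine only, and none of the three phenserine regimens in Section 6.1 is once daily. The 24 h figure applies to nobody in that arm.

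**The case against.** **The instructions inside Section 4.4.1 can be reconciled.** The words about continuing with the next scheduled dose belong to the omitted-dose branch. Nothing says that a late dose must be followed by a dose at the original time, so the minimum-interval bullet may be meant to govern. This stands. Within the section the fault is silence on the point, not an outright contradiction. It does not remove the conflict with the diary, which expressly accepts an interval 2 h short.

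**The diary permits a shorter gap but does not require one.** This also stands. A reader might infer that a participant must break one rule to keep the other. That is not so: a gap of 8 h or 12 h satisfies both texts.

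**The exposure effect may be small.** As an illustration, assume instantaneous absorption and first-order elimination with the 6.53 h half-life in Section 2.3.1. The fraction of a dose remaining is 0.5^(8/6.53) = 0.428 at 8 h and 0.5^(6/6.53) = 0.529 at 6 h. The steady-state peak on 10 mg every 8 h is 10/(1 − 0.428) = 17.48 mg-equivalents. After one 6 h gap it is 10 + 17.48 × 0.529 = 19.2, about 10% higher. For 15 mg twice daily, which Section 2.3.1 describes as acceptably tolerated, the same model gives 0.5^(12/6.53) = 0.280 and 15/(1 − 0.280) = 20.8. Section 2.3.1 also reports no accumulation over 6 days of once- or twice-daily dosing; three-times-daily dosing was not in that study. This stands as a reason not to claim a demonstrated harm. It is a crude model, and it does not show that any particular interval is acceptable.

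**Compliance is barely touched.** A late dose still counts as taken. One omitted capsule in Weeks 5 to 8 is 1 of 3 × 28 = 84, or 1.2%, against an 80–120% window. This stands.

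**There is support at home and on site.** Staff explain dosing at each visit (Section 4.4), study partners remind participants and help to document delays (Section 4.4.3), and the diary suggests a pill box and phone reminders. These help adherence, but they do not settle which interval staff and partners should teach.

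**Conclusion.** The two texts conflict as written. The diary accepts 6 h where Section 4.4.1 sets a minimum of 8 h, and 10 h where it sets 12 h. The shortfall is up to 2 h on every phenserine regimen, and all 12 planned phenserine participants would receive the instruction. The once-daily figure matches no phenserine regimen. The conclusion rests on the plain reading of the diary, in which the tolerance applies to the interval.

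Three stronger readings are not supported.

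- A reader might infer that the diary allows gaps of 4 h on three doses a day (8 − 2 − 2), or 8 h on two (12 − 2 − 2). That requires applying the tolerance to the clock time of each dose, with a late dose followed by an early one. The diary does not say this.
- A reader might estimate drug carry-over from the 8.25 h in Section 4.5. That section describes it as a half-life of AChE inhibition, so it does not measure drug remaining.
- A reader might conclude that peak exposure, escalation or compliance will be distorted. Such effects are plausible, but the documents do not establish them. Any effect on the primary biomarker comparison is indirect.

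The point should be corrected because it concerns a rule the protocol itself presents as a safety rule, and because participants with cognitive impairment need one consistent instruction.

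**What to change.** 1. Reconcile the minimum interval and the late-dose rule in Section 4.4.1 with the diary tolerance in Appendix 7, so that one mutually compatible set of intervals appears in both.
2. State in both places whether a late dose moves the next dose, and whether lateness is then judged against the original or the moved schedule.
3. Reconcile the once-daily line in Section 4.4.1 with the phenserine regimens in Section 6.1.

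The choice of interval belongs to the clinical team; none is proposed here. The cost is a few lines in Section 4.4.1 and a new diary version. Visits, drug supply and sample size do not change.
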